Symptomatic Progression			X		X		X	X	X	
Assess:
 
 
• Symptomatic skeletal event defined as symptomatic fracture, surgery, or radiation to bone or spinal cord compression
 
• Pain progression or worsening of disease-related symptoms requiring initiation of a new systemic anti-cancer therapy
 
• Development of clinically significant symptoms due to loco-regional tumor progression requiring surgical intervention or radiation therapy
 
 
Perform until evidence of symptomatic disease progression, start of new anticancer therapy, withdrawal of consent, death, or study completion, whichever occurs first.

Study Treatment										

Screening, On-Treatment and Post-Treatment Schedule of Activities										
Study phases	Screening		On Treatment Cycle duration = 28 days				Post-Treatment Follow-up		Instructions	
	Baseline		Cycle 1		Cycle 2		Cycle 3 and subsequent	Short-Term Follow-Up a	Long-Term Follow-Up b	Instructions
Relative Day within Dosing Cycle & Visit Window ( $\pm n$ days)	$\le 28$	$\le 14$	D1 ( $\pm 3$ )	D15 ( $\pm 3$ )	D1 ( $\pm 3$ )	D15 ( $\pm 3$ )	D1 ( $\pm 3$ )	V801 (30 days $\pm 7$ )	V802-8XX (90 days $\pm 14$ )	Procedures and disease assessments (tumor imaging) should be performed as per the schedule of activities, according to the calendar days, regardless of treatment delays.
Abemaciclib			Orally twice daily, on Days 1 through 28 of a 28-day cycle.						See Section 6.1	
Study Drug Compliance Assessment				X			X			
Review Patient Diary			X	X	X	X				Review patient diary at each study visit for completion of date and time for each dose taken on the day before PK sampling. After Cycle 3 Day 1, the diary is no longer required.
Post-study Treatment Collections										
Post-Discontinuation Anti-Cancer Therapies							X	X	Collect until death, withdrawal of consent, or study completion.	
Survival Status							X	X	Although preferable to collect during a clinic visit, if no procedures are required, survival information may be collected by contacting the patient or family directly (e.g., via telephone. This should be collected at minimum every 90 ( $\pm 14$ ) days if no other procedures are performed.	

Screening, On-Treatment and Post-Treatment Schedule of Activities									
Study phases	Screening		On Treatment Cycle duration = 28 days			Post-Treatment Follow-up		Instructions	

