#### **9.4.3. Secondary endpoint(s)**

Summaries of event rates, including radiologic ORR, and PSA-based response, will be defined as the proportion of all treated participants who achieve the specified response category.

Participants with a non-evaluable or unknown response per specified criteria will be considered non-responders for the purpose of calculating the response rate.

Detailed censoring rules for time to event (TTE) endpoints are described in the SAP. For all TTE endpoints, median event times and rates at various time points, with 95% CI, will be estimated using the Kaplan-Meier method (Kaplan and Meier 1958). Sensitivity analyses for TTE will be described in the SAP.

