6.7.2. Secondary Efficacy Analyses

6.7.2.1. Radiographic Progression-Free Survival

The radiographic progression-free survival (rPFS) time is measured from the date of first dose to the earliest date of investigator-determined radiographic disease progression (by objective radiographic disease assessment per RECIST 1.1 for soft tissue AND/OR radionuclide bone scan using PCWG3 criteria for bone) or death from any cause, whichever occurs first. Patients who have neither progressed nor died will be censored at the day of their last radiographic tumor assessment (if available) or date of first dose if no postinitiation (ie, postbaseline) radiographic assessment is available. The detailed censoring rules are described in [Table JPCY.6.1](#).

Radiographic progression-free survival will be summarized and listed for all treated patients. The Kaplan-Meier (KM) method (Kaplan and Meier 1958) will be used to estimate the rPFS curve as well as rPFS rates at 3, 6, 9, and 12 months.

Table JPCY.6.1. rPFS Event/Censoring Scheme

Situation ^a	Event/Censor	Date of Event or Censor
Radiographic disease progression or death	Event	Earliest date of radiographic disease progression or death ^b
No radiographic disease progression and no death	Censored	Date of last adequate radiographic assessment showing no evidence of disease progression or date of first dose (whichever is later) ^c
Unless		
No baseline radiographic tumor assessment available	Censored	Date of first dose
No adequate postbaseline radiographic tumor assessment available and death reported after 2 scan intervals following first dose ^{c,d}	Censored	Date of first dose
New anticancer treatment started and no radiographic disease progression or death within 14 days	Censored	Date of last adequate radiographic assessment showing no evidence of disease progression prior to (start of new therapy +14 days) or date of first dose (whichever is later) ^c
Radiographic disease progression or death documented after 2 or more scan intervals following last adequate radiographic tumor assessment or first dose (whichever is later) ^{c,d}	Censored	Date of last adequate radiographic assessment showing no evidence of disease progression or date of first dose (whichever is later) ^c

Abbreviations: CR = complete response; PD = progressive disease; PR = partial response; rPFS = radiographic progression-free survival; SD = stable disease.

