6.7.2.7. Time to Symptomatic Progression

Time to symptomatic progression is defined as the time from first dose to any of the following (whichever occurs earlier):

- symptomatic skeletal event, defined as symptomatic fracture, surgery or radiation to bone, or spinal cord compression
- pain progression or worsening of disease-related symptoms requiring initiation of a new systemic anticancer therapy, and
- development of clinically significant symptoms due to locoregional tumor progression requiring surgical intervention or radiation therapy.

For patients not known to have had symptomatic progression at the time of data analysis, data will be censored on the last date at which no symptomatic progression is indicated.

Time to symptomatic progression will be summarized and listed for all treated patients. A KM analysis will be performed to estimate the time to symptomatic progression survival curve as well as quartiles and rates at 3-month intervals. As appropriate, these analyses will be repeated for each of the individual components of time to symptomatic progression.

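### Kaplan-Meier for time to symptomatic progression censors men who die first, so the complement of its event-free rates is at or above the proportion who have the event

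*SAP*

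**What the plan says.** SAP 6.7.2.7 measures time from first dose to the earliest of three outcomes: a symptomatic skeletal event, pain or symptom worsening that leads to new systemic therapy, or loco-regional symptoms that need surgery or radiation. Death is not among them, and Protocol 8.1.1 also omits it. For patients with no known event, "data will be censored on the last date at which no symptomatic progression is indicated". There is no separate rule for men who die.

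The estimator is Kaplan-Meier (KM): "A KM analysis will be performed to estimate the time to symptomatic progression survival curve as well as quartiles and rates at 3-month intervals". Where appropriate, "these analyses will be repeated for each of the individual components of time to symptomatic progression". Protocol 9.4.3 sets the same approach in general: "For all TTE endpoints, median event times and rates at various time points, with 95% CI, will be estimated using the Kaplan-Meier method".

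The Schedule of Activities (Protocol 1.3) fixes when observation ends: "Perform until evidence of symptomatic disease progression, start of new anticancer therapy, withdrawal of consent, death, or study completion, whichever occurs first".

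Radiographic progression-free survival (SAP 6.7.2.1) differs because its event includes progression "or death from any cause, whichever occurs first". No competing-risk method is named in the visible text. The one sensitivity analysis listed in SAP 6.7.3 is central review of imaging endpoints.

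**The concern.** KM treats a censored patient as still at risk of the event after he leaves observation. That is reasonable for a man whose follow-up has simply not run long enough. It is not reasonable for a man who has died, because he cannot go on to have a symptomatic event. SAP 6.7.2.7 does not say in words that deaths are censored, but a definition without death and a catch-all censoring rule have that effect.

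The planned rates are event-free rates, so the problem lies in their complement. If 1 − KM at 6 or 12 months is taken as the share of treated men with symptomatic progression, it is too high. The quartiles shift in the same direction. In a single-arm study the estimates themselves are the result for this endpoint, and the schema (Protocol 1.2) lists it among the key secondary endpoints.

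The component analyses have a second problem. Assessment stops at the first symptomatic progression, so a man whose first event is of one type is no longer observed for the others. The other components then compete in the same way as death does.

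**Working it through.** The plan gives no rate, event count or precision for symptomatic progression, so there is no stated figure to reproduce.

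**Inputs (all hazards are assumed and constant)**
- Symptomatic progression: h = 0.08 per month.
- Death without symptomatic progression: d = 0.02, 0.04 or 0.06 per month.
- Scale check on d: Protocol 4.2 cites median overall survival of 11.0 months in one arm of an earlier-line trial. That implies a total death hazard of ln 2 / 11.0 = 0.063. The top value of d is therefore about the whole of that hazard, not just the part due to death without a prior symptomatic event.

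**Formulas**
- KM complement with deaths censored: 1 − exp(−h·t).
- Actual proportion with the event (cumulative incidence): h/(h+d) × [1 − exp(−(h+d)·t)].

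**Composite endpoint**

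6 months, KM complement: 1 − exp(−0.48) = 38.1%.
- d = 0.02: 0.800 × [1 − exp(−0.60)] = 36.1%, gap 2.0 points.
- d = 0.04: 0.667 × [1 − exp(−0.72)] = 34.2%, gap 3.9 points.
- d = 0.06: 0.571 × [1 − exp(−0.84)] = 32.5%, gap 5.6 points.

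12 months, KM complement: 1 − exp(−0.96) = 61.7%.
- d = 0.02: 0.800 × [1 − exp(−1.20)] = 55.9%, gap 5.8 points.
- d = 0.04: 0.667 × [1 − exp(−1.44)] = 50.9%, gap 10.8 points.
- d = 0.06: 0.571 × [1 − exp(−1.68)] = 46.5%, gap 15.2 points.

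**Median.** The KM median is ln 2 / 0.08 = 8.7 months. Setting the cumulative incidence to 50% and solving for t gives:
- d = 0.02: −ln(0.375)/0.10 = 9.8 months.
- d = 0.04: −ln(0.25)/0.12 = 11.6 months.
- d = 0.06: −ln(0.125)/0.14 = 14.9 months.

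**A wider set of assumptions.** Take a median time to symptomatic progression of 6 to 24 months, and d at 25% to 100% of the hazard implied by the cited median survivals of 11.0 and 13.6 months. The 12-month gap then runs from about 2 points (29.3% against 27.3%) to about 18 points (75.0% against 57.1%).

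**Components.** Assume a 50/30/20 split of first events, a 12-month composite median (h = ln 2 / 12) and d = 0.5 × ln 2 / 11.0. At 12 months:
- KM complements: 29.3%, 18.8% and 12.9%, sum 61.0%.
- Cumulative incidences: 21.3%, 12.8% and 8.5%, sum 42.5% after rounding, which equals the composite cumulative incidence.
- Composite KM complement: 50.0%.

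The component KM figures exceed the true values by factors of 1.38, 1.47 and 1.52, against 50.0/42.5 = 1.18 for the composite. They also do not add up to the composite.

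**Simulation check.** In 2,000 runs with 40 patients, a 12-month median and d at 50% or 100% of the 11.0-month hazard, Aalen-Johansen averaged 42.5% and 36.8% at 12 months (true values 42.5% and 36.6%). KM averaged 50% when censoring at death. It averaged 51.5% and 52.1% when censoring at the last 28-day visit, which is closer to the SAP's rule.

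**The case against.** The strongest reply is that KM on the event alone is a recognised descriptive quantity. The SAP speaks of a survival curve and event-free rates, and nowhere says they are to be read as the share of men affected. That is fair, and it is why the point concerns the complement and the reading of the median. It does not remove the point. A KM curve describes a setting without death only if death is independent of symptomatic progression, and the SAP neither states that aim nor defends that assumption.

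The size is also open to challenge. A reader might infer that death before a symptomatic event is common here, and that the rates will be inflated by 15 points. The documents do not support either inference. They give no rate of death without prior symptomatic progression, and the 15-point figure needs a death hazard near the whole of that in the cited trial. Entry also requires ECOG 0–1 (inclusion criterion 10) and excludes estimated life expectancy under 4 months (exclusion criterion 20). Against that, this population is later-line and may die faster. The size is unknown rather than shown to be small.

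Timing matters too. The primary analysis comes about 6 months after the last patient enters (Protocol 9.4.2), so only earlier enrollees will have reached 12 months and the 6-month gap is the more relevant one then. With complete follow-up of 40 men, a 95% interval around 50% is about ±1.96 × √(0.25/40) = ±15 points. Sampling error of that size limits the practical effect but does not cancel a bias that has one direction.

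Three further replies have some force. Component analyses are conditional, so their bias arises only if they are run. The exploratory analyses are redacted, so a method for a related endpoint may exist out of sight. SAP 6.1.2 allows alternative methods when assumptions fail, and patient listings would let deaths be traced, but both are discretionary and neither replaces a stated method.

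Finally, death is not the only difficulty. Assessment also ends at the start of new anticancer therapy (Protocol 1.3 and 7.1), and in the cited trial 53.5% of the cabazitaxel arm received subsequent treatment (Protocol 4.2). Aalen-Johansen alone does not remove that informative censoring. This objection stands, and the change below has to address it.

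**Conclusion.** The point holds as a low-cost improvement to a descriptive secondary endpoint. The direction follows from the plan's own definition and censoring rule: with deaths censored, 1 − KM cannot fall below the cumulative incidence, and it lies above it once some men die first and others have events later. Reading the same direction against the actual proportion of men also requires the remaining censoring to be uninformative, which is doubtful where new therapy ends assessment.

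Under the assumed hazards the overstatement is about 2 to 6 points at 6 months and 6 to 15 at 12 months. These figures illustrate the effect and do not predict this trial's results. The effect on components is proportionally larger, if those analyses are done.

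Nothing here bears on the objective response rate or on whether the study is declared positive. Nor does it make the planned KM curve invalid. The curve answers a different question from the proportion of men affected, and the SAP does not say which question is meant.

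**What to change.** In SAP 6.7.2.7:

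1. State that death without symptomatic progression is a competing event.
2. Report Aalen-Johansen cumulative incidence, with 95% confidence intervals, at the same 3-month time points beside the planned KM estimates. Label the KM rates as event-free estimates with deaths censored.
3. For any component analysis, treat death and the other components as competing events.
4. State how the start of new anticancer therapy without symptomatic progression, and any death after it, is handled, and note that Aalen-Johansen does not by itself remove that informative censoring.

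Survival status and dates of subsequent therapy are already collected, so no new data are needed. Because KM is kept, Protocol 9.4.3 is still met. Protocol 9.4.1 requires an amendment only when a principal feature changes, which this is not. The cost is SAP wording and one added standard analysis, whose intervals will be wide with about 40 patients.

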6.7.3. Sensitivity Analyses

Sensitivity analyses will be undertaken for calculation of the primary or key secondary endpoints in order to evaluate the robustness of the analysis. The following sensitivity analysis will be performed:

- **Blinded Independent Central Review** - as appropriate, imaging-based endpoints (including ORR, DoR, and rPFS) will also be assessed by a blinded independent review of centrally stored imaging.

6.7.4. *Exploratory Analyses*

CCI

6.8. **Health Outcomes/Quality-of-Life Analyses**

Patient-reported outcomes (PRO) are measured through the following:

- single-item worst Pain Numerical Rating Scale (NRS)
- the National Cancer Institute's PRO version of the Common Terminology Criteria for Adverse Events version 5.0 (CTCAE) (PRO-CTCAE)
- item GP5 of the Functional Assessment of Cancer Therapy-General (FACT-G), and
- European Organization for the Research and Treatment of Cancer Quality of Life Questionnaire (EORTC QLC-C30).

Additionally, analgesic use will be classified into categories (eg, according to the WHO analgesic ladder or the Analgesic Quantification Algorithm scale).

For each instrument, the compliance rate will be calculated by visit. Reasons for noncompliance will also be summarized.

CCI

6.9. **Bioanalytical and Pharmacokinetic/Pharmacodynamic Methods**

Pharmacokinetic (PK) and pharmacodynamic analyses will be performed according to a separate PK analysis plan.

6.10. **Biomarker Analyses**

Protocol Section 8.8 describes the biomarker samples that will be collected during the course of the study and will be used to carry out biomarker-specific exploratory analyses. In addition to characterizing the biomarker data distribution, these analyses may include the assessment of prognostic or predictive relationships between the biomarker(s) being investigated and the clinical efficacy endpoints of the study.

In particular, the percentage of cells expressing Ki-67 by immunohistochemistry for each participant in the biomarker-evaluable population will be summarized and listed. Additionally, Ki-67 expression values will be classified into a series of binary variables (eg, <10%, <25%, etc.), and the proportion of participants in each group will be reported with corresponding exact 95% CIs.

If deemed necessary, further analysis of biomarkers may be described in a separate biomarker SAP.

6.11. Safety Analyses

Safety analyses will be completed on the safety population as specified below, unless COVID-19 impact creates a situation requiring a change to an existing analysis or a need for additional analyses as outlined by Nilsson et al. (2020).

6.11.1. Extent of Exposure

Drug exposure, drug adjustments, and omissions for abemaciclib will be summarized for all treated patients. Drug exposure will include summaries of cycles received per patient, duration on therapy, and cumulative dose. The summary of dose adjustments and omissions will include the reason for adjustment or omission. Dose intensity will be summarized for all treated patients. Dose intensity will be calculated as the actual cumulative amount of drug taken divided by the duration of treatment. Relative dose intensity will be calculated as the actual amount of drug taken divided by the amount of drug assigned times 100% (ie, expressed as a percentage).

Extent of exposure will be measured by pill counts. Dose intensity will be expressed in mg/day. The assigned cumulative dose for abemaciclib while on study is

- 200 mg per dose × 2 doses per day × number of days on study drug.

6.11.2. Adverse Events

Adverse event verbatim text will be mapped by the sponsor or designee to corresponding terminology within the MedDRA. Severity grades will be assigned by the investigator using CTCAE version 5.0. Medical Dictionary for Regulatory Activities PTs, identified by Medical as clinically identical or synonymous, will be grouped together under a single, consolidated PT. For example, 'Neutropenia' and 'Neutrophil count decreased' will be reported as 'Neutropenia'. Adverse events will be reported according to PTs resulting from this process.

Preexisting conditions are defined as AEs that begin prior to the first dose of study drug.

A treatment-emergent adverse event (TEAE) is defined as any AE that begins between the day of first dose and 30 days after treatment discontinuation (or up to any time if serious and related to study treatment) or any preexisting condition that increases in CTCAE version 5.0 grade between the day of first dose and 30 days after treatment discontinuation (or up to any time if serious and related to study treatment).

The MedDRA Lowest-Level Term will be used for comparisons of preexisting conditions to on-treatment events in the treatment-emergent computation.

A serious adverse event (SAE) is any AE during this study that results in one of the following outcomes:

- death
- initial or prolonged inpatient hospitalization

- a life-threatening experience (ie, immediate risk of dying)
- persistent or significant disability/incapacity
- congenital anomaly/birth defect, and
- is considered significant by the investigator for any other reason.

Important medical events that may not result in death, be life-threatening, or require hospitalization may be considered SAEs when, based on appropriate medical judgment, they may jeopardize the patient and may require medical or surgical intervention to prevent one of the outcomes listed in this definition.

The following AE listings and summaries will be produced:

- Overview of TEAEs
- Summary of TEAEs by PT (all grade and Grade ≥ 3)
- Summary of TEAEs by System Organ Class (SOC) and PT (all grade and Grade ≥ 3)
- Summary of TEAEs by PT and maximum grade (1-5)
- List of SAEs
- Summary of SAEs by SOC and PT (all grade and grade ≥ 3), and
- Summary of AEs as reason for study treatment discontinuation by PT.

The TEAE and SAE summaries will be produced for all TEAEs/SAEs and repeated for TEAEs/SAEs related to study treatment, where relationship of the AE to the study treatment will be assessed by the investigator (yes or no).

6.11.3. Deaths

All deaths on study not attributed to study disease by the investigator will be listed along with the reason for death, if known. For those deaths attributed to an AE, the listing will include the PT of the AE. A summary of deaths including reasons for death will be produced.

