#### **8.2.2.4. Guidance for Interstitial Lung Disease/Pneumonitis**

Interstitial lung disease (ILD)/pneumonitis has been identified as an adverse drug reaction for abemaciclib. The majority of events observed in clinical trials were Grade 1 or Grade 2 with serious cases and fatal events reported. Additional information is available in the IB.

Ask your participants to report any new or worsening pulmonary symptoms, such as dyspnea, cough, and fever, and investigate and treat as per your local clinical practice (including corticosteroids as appropriate). If ILD/pneumonitis is suspected, investigations may include imaging, such as high-resolution CT, bronchoalveolar lavage, and biopsy as clinically indicated. Refer to Section 6.6.2 for guidance on dose adjustments of abemaciclib for patients with ILD/pneumonitis (see Section 10.7, Appendix 7, for ILD/pneumonitis CTCAE grades). Discontinue abemaciclib in cases of severe (Grade 3 or 4) ILD/pneumonitis.

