### **8.3.1. Time Period and Frequency for Collecting AE and SAE Information**

All SAEs will be collected from the signing of the ICF until participation in study has ended.

All AEs will be collected from the signing of the ICF until the short-term 30-day follow-up visit.

Adverse events that begin before the start of study intervention but after signing of the ICF will be recorded on the Adverse Event CRF. Although all AEs after signing the ICF are recorded by the site in the CRF/electronic data entry, SAE reporting to the sponsor begins after the participant has signed the ICF and has received study drug. However, if an SAE occurs after signing the ICF, but prior to receiving abemaciclib, it needs to be reported ONLY if it is considered reasonably possibly related to study procedures.

All SAEs will be recorded and reported to the sponsor or designee immediately and under no circumstance should this exceed 24 hours, as indicated in Section 10.3, Appendix 3. The investigator will submit any updated SAE data to the sponsor within 24 hours of it being available. Serious adverse events, including death, caused by disease progression should not be reported unless the investigator deems them to be possibly related to study intervention.

Investigators are not obligated to actively seek AEs or SAEs after conclusion of the study participation (the participant summary CRF has been completed). However, if the investigator learns of any SAE, including a death, at any time after a participant has been discharged from the study, and he/she considers the event to be reasonably related to the study intervention or study participation, the investigator must promptly notify the sponsor.

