#### **9.4.4. Exploratory endpoint(s)**

**CCI**

#### **9.4.5. Other Safety Analyses**

All safety analyses will be made on the Safety Population, defined as all participants who receive at least 1 dose of study drug will be evaluated for safety and toxicity.

The Medical Dictionary for Regulatory Activities (MedDRA®) Version [21.0 (or higher)] will be used when reporting AEs by MedDRA terms. The MedDRA Lower Level Term (LLT) will be used in the treatment-emergent computation. Treatment-emergent adverse events (TEAEs) will be summarized by System Organ Class (SOC) and by decreasing frequency of Preferred Term (PT) within SOC.

Safety analyses will include summaries of the following:

- TEAEs, including severity and possible relationship to study drug
- Treatment-emergent SAEs, including possible relationship to study drug
- AEs leading to dose adjustments
- discontinuations from study intervention due to adverse events or death
- treatment-emergent abnormal changes in laboratory values
- treatment-emergent abnormal changes in vital signs

The number of participants with dose reductions, dose delays, or dose omissions will be summarized, as will the reasons for dose adjustments.

Reasons for death will be summarized separately for on-therapy and within 30 days of treatment discontinuation.

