6.7.2.2. Overall Survival

The overall survival (OS) time is measured from the date of first dose to the date of death from any cause. If the patient is alive or lost to follow-up at the time of data analysis, OS data will be censored on the last date the patient is known to be alive. Overall survival will be summarized

and listed for all treated patients. The KM method (Kaplan and Meier 1958) will be used to estimate the OS curve as well as OS rates at 3, 6, 9, 12, and 18 months.

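### The SAP's death listing leaves out deaths attributed to disease, and its death summary omits the timing split that the protocol requires

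*SAP*

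**What the plan says.** SAP 6.11.3 plans two outputs on deaths. The first is a listing restricted by attribution: "All deaths on study not attributed to study disease by the investigator will be listed along with the reason for death, if known". Where such a death is attributed to an adverse event, the listing names the preferred term. The second is a table: "A summary of deaths including reasons for death will be produced". The table is not restricted by cause, and no time categories are given for it.

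Protocol 9.4.5 is more specific about timing: "Reasons for death will be summarized separately for on-therapy and within 30 days of treatment discontinuation".

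Protocol 8.3.1 sets the rule for SAE reporting: "Serious adverse events, including death, caused by disease progression should not be reported unless the investigator deems them to be possibly related" to study intervention. Protocol 10.3.2 gives death from progression as an example of an event that cannot be an SAE, because it is not an adverse event in the first place.

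Two efficacy sections also bear on the point. Overall survival is to be summarised "and listed for all treated patients. The KM method (Kaplan and Meier 1958) will be used to estimate the OS curve" (SAP 6.7.2.2). For rPFS, in which death from any cause is an event, SAP 6.7.2.1 says: "Radiographic progression-free survival will be summarized and listed for all treated patients".

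**The concern.** The trial is open-label and single-arm, with no data monitoring committee (protocol 6.3 and 9.6). With no control arm to compare against, early deaths are best judged one by one: when the death happened in relation to dosing, and what the investigator thought caused it.

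Under the SAP, a single judgement by an unblinded investigator decides whether a death reaches the safety listings. If the death is put down to disease and not considered possibly related to the drug, it falls outside the death listing through the SAP's filter. It normally falls outside the SAE list too, through the protocol's reporting rule. The protocol notes interstitial lung disease/pneumonitis with this drug, "with serious cases and fatal events reported". In heavily pretreated metastatic disease, the line between a drug-related respiratory death and a disease death may not always be clear. These are the cases that a reader of the safety report would want to see individually.

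Timing is the second issue. Survival status is collected every 3 months until death (protocol 7.1), so the death summary can include deaths long after treatment stopped. The protocol's split exists to keep the early deaths distinguishable, and the SAP does not repeat it.

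**Working it through.** No arithmetic applies. The check sets the passages side by side and follows a death through each planned output.

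**Step 1: timing.** Protocol 9.4.5 names two windows, on therapy and the 30 days after discontinuation. SAP 6.11.3 names none, and no other SAP section restores them. Protocol 9.4.1 describes the SAP as the more detailed account and says that changes of method, with their justification, will be described in the SAP and the clinical study report. The SAP gives no justification here, and on deaths it is the less detailed of the two documents.

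**Step 2: two deaths during treatment.** Death A is attributed to progression and not considered possibly related. Death B is recorded as a fatal adverse event.

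| Planned output | Death A | Death B |
|---|---|---|
| Death listing (SAP 6.11.3) | Not listed | Listed, with preferred term |
| SAE list (SAP 6.11.2; protocol 8.3.1, 10.3.2) | Normally not listed | Listed |
| Treatment-emergent events by maximum grade (SAP 6.11.2) | Death not shown; an event recorded before death could appear at its own grade | Shown as Grade 5 |
| Summary of deaths with reasons (SAP 6.11.3) | Counted; no window specified | Counted; no window specified |
| Overall survival listing (SAP 6.7.2.2) | Listed, timed from first dose | Listed, timed from first dose |
| rPFS listing (SAP 6.7.2.1) | Patient listed; death is the event only if no radiographic progression came first and no censoring rule applies | Same |

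**Step 3: what the remaining outputs say about Death A.** The death table gives a reason but no specified timing. The overall survival listing gives time from first dose, but the SAP does not say that it gives the cause of death or the time since last dose. No single planned output is stated to give cause and time since last dose together for this death.

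**Step 4: what is missing for timing.** The treatment-emergent window runs from first dose to 30 days after discontinuation, longer for serious related events. Fatal adverse events are therefore covered over roughly the period that protocol 9.4.5 has in mind. That table does not separate on-therapy deaths from those in the following 30 days, and it does not contain deaths classed as progression.

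**The case against.** The strongest reply is that little is hidden. Every treated patient has a line in the overall survival listing, so a reader who infers that Death A is listed nowhere goes beyond the documents. Nor do they support the reading that no output shows fatal events by exposure window: the maximum-grade table includes Grade 5 treatment-emergent events. A fatal pneumonitis recorded as such appears there, in the SAE list and in the death listing. SAP 6.3 summarises reasons for stopping treatment, and protocol 9.4.5 includes discontinuations due to death. The gap therefore needs a death that has been attributed to disease, and removing a filter does not correct a wrong attribution.

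A reader might also infer that the SAP pools early deaths with late ones. It does not say so. It leaves the windows unspecified, which would permit pooling, but the protocol's requirement still stands.

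Finally, the listing filter contradicts nothing in the protocol, which asks for a summary of reasons and not a listing of all deaths.

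All of this stands, and it limits the point. Two things remain. The timing split is a protocol requirement that the SAP omits without explanation. The listing filter makes review of individual early deaths depend on unblinded attribution. A full listing would not settle attribution, but it would let someone else look at it.

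**Conclusion.** The point holds as a limited safety-reporting discrepancy. The omission of the protocol 9.4.5 split is a plain difference between the documents. The restricted listing is a design choice in the SAP. Combined with the SAE reporting rule, it removes progression-attributed deaths from the safety death listing and normally from the SAE list.

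The word normally matters: a progression death that the investigator considers possibly related is reported as an SAE. The conclusion also assumes that the overall survival and rPFS listings carry only what the SAP describes. If they were programmed to include cause of death and time since last dose, most of the listing gap would close.

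I give no numerical size. The share of deaths falling in the early window would depend on survival, treatment duration and length of follow-up at the analysis. Neither document gives a planning median for survival or time on treatment in this trial. The point does not need such a figure. No endpoint, decision rule or data collection is affected.

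**What to change.** Amend SAP 6.11.3 in two places.

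- **Listing.** List all deaths regardless of attribution. For each, give the investigator-assigned cause, days from first dose and days from last dose, and keep the preferred term where an adverse event was the cause.
- **Summary.** Produce the protocol 9.4.5 summary of reasons for death, with separate columns for deaths on therapy and deaths within 30 days of discontinuation. Show later deaths in a column of their own; that third column is an addition to the protocol's two windows. If the sponsor means to drop the split, the SAP should say so and give the reason.

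The cost is one longer listing and extra table columns. Dosing records, discontinuation dates and survival status are already collected under the protocol (6.4, 7.1 and the Schedule of Activities), and the SAP already plans to report reasons for death. No new assessment is needed.
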